10. MANAGEMENT AND REPORTING OF ADVERSE EVENTS/ADVERSE REACTIONS

Safety event	Recorded on the case report form	Reported on the NIS AEM Report Form to Pfizer Safety within 24 hours of awareness
SAE	All	All
Non-serious AE	All	None
Scenarios involving exposure to a drug under study, including exposure during pregnancy, exposure during breast feeding, medication error, overdose, misuse, extravasation; lack of efficacy; and occupational exposure	All (regardless of whether associated with an AE), except occupational exposure	All (regardless of whether associated with an AE)

For each AE, the investigator must pursue and obtain information adequate both to determine the outcome of the adverse event and to assess whether it meets the criteria for classification as a SAE (see section "Serious Adverse Events" below)

Safety events listed in the table above must be reported to Pfizer within 24 hours of awareness of the event by the investigator **regardless of whether the event is determined by the investigator to be related to a drug under study**. In particular, if the SAE is fatal or life-threatening, notification to Pfizer must be made immediately, irrespective of the extent

of available event information. This timeframe also applies to additional new (follow-up) information on previously forwarded safety event reports. In the rare situation that the investigator does not become immediately aware of the occurrence of a safety event, the investigator must report the event within 24 hours after learning of it and document the time of his/her first awareness of the events.

For those safety events that are considered serious or that are identified in the far right column of the table above that are reportable to Pfizer within 24 hours of awareness, the investigator is obligated to pursue and to provide any additional information to Pfizer in accordance with this 24-hour timeframe. In addition, an investigator may be requested by Pfizer to obtain specific follow-up information in an expedited fashion. This information is more detailed than that recorded on the case report form. In general, this will include a description of the adverse event in sufficient detail to allow for a complete medical assessment of the case and independent determination of possible causality. Any information relevant to the event, such as concomitant medications and illnesses must be provided. In the case of a patient death, a summary of available autopsy findings must be submitted as soon as possible to Pfizer or its designated representative.

Reporting period

For each patient, the safety event reporting period begins at the time of the patient's first dose of 3rd line treatment or the time of the patient's informed consent if s/he is already exposed to 3rd line treatment, and lasts through the end of the observation period of the study, which must include at least 28 calendar days following the last administration of a drug under study; a report must be submitted to Pfizer Safety (or its designated representative) for any of the types of safety events listed in the table above occurring during this period.

If the investigator becomes aware of a SAE occurring at any time after completion of the study and s/he considers the SAE to be related to 3rd line treatment, the SAE also must be reported to Pfizer Safety.

Causality assessment

The investigator is required to assess and record the causal relationship. For all AEs, sufficient information should be obtained by the investigator to determine the causality of each adverse event. For AEs with a causal relationship to 3rd line treatment, follow-up by the investigator is required until the event and/or its sequelae resolve or stabilize at a level acceptable to the investigator, and Pfizer concurs with that assessment.

An investigator's causality assessment is the determination of whether there exists a reasonable possibility that 3rd line treatment caused or contributed to an adverse event. If the investigator's final determination of causality is "unknown" and s/he cannot determine whether 3rd line treatment caused the event, the safety event must be reported within 24 hours.

If the investigator cannot determine the etiology of the event but s/he determines that *3rd line treatment* did not cause the event, this should be clearly documented on the case report form and the NIS AEM Report Form.

DEFINITIONS OF SAFETY EVENTS

Adverse events

An AE is any untoward medical occurrence in a patient administered a medicinal product. The event need not necessarily have a causal relationship with the product treatment or usage. Examples of adverse events include but are not limited to:

- Abnormal test findings (see below for circumstances in which an abnormal test finding constitutes an adverse event);
- Clinically significant symptoms and signs;
- Changes in physical examination findings;
- Hypersensitivity;
- Lack of efficacy;
- Drug abuse;
- Drug dependency.

Additionally, for medicinal products, they may include the signs or symptoms resulting from:

- Drug overdose;
- Drug withdrawal;
- Drug misuse;
- Off-label use;
- Drug interactions;
- Extravasation;
- Exposure during pregnancy;
- Exposure during breast feeding;
- Medication error;

- Occupational exposure.

Abnormal test findings

The criteria for determining whether an abnormal objective test finding should be reported as an adverse event are as follows:

- Test result is associated with accompanying symptoms, and/or
- Test result requires additional diagnostic testing or medical/surgical intervention, and/or
- Test result leads to a change in study dosing or discontinuation from the study, significant additional concomitant drug treatment, or other therapy, and/or
- Test result is considered to be an adverse event by the investigator or sponsor.

Merely repeating an abnormal test, in the absence of any of the above conditions, does not constitute an adverse event. Any abnormal test result that is determined to be an error does not require reporting as an adverse event.

Serious adverse events

A serious adverse event is any untoward medical occurrence in a patient administered a medicinal or nutritional product (including pediatric formulas) at any dose that:

- Results in death;
- Is life-threatening;
- Requires inpatient hospitalization or prolongation of hospitalization (see below for circumstances that do not constitute adverse events);
- Results in persistent or significant disability/incapacity (substantial disruption of the ability to conduct normal life functions);
- Results in congenital anomaly/birth defect.

Progression of the malignancy under study (including signs and symptoms of progression) should not be reported as a serious adverse event unless the outcome is fatal within the safety reporting period. Hospitalization due to signs and symptoms of disease progression should not be reported as a serious adverse event. If the malignancy has a fatal outcome during the study or within the safety reporting period, then the event leading to death must be recorded as an adverse event and as a serious adverse event with severity Grade 5.

Medical and scientific judgment is exercised in determining whether an event is an important medical event. An important medical event may not be immediately life-threatening and/or result in death or hospitalization. However, if it is determined that the event may jeopardize the patient or may require intervention to prevent one of the other outcomes listed in the definition above, the important medical event should be reported as serious.

Examples of such events are intensive treatment in an emergency room or at home for allergic bronchospasm; blood dyscrasias or convulsions that do not result in hospitalization; or development of drug dependency or drug abuse.

Additionally, any suspected transmission via a Pfizer product of an infectious agent, pathogenic or non-pathogenic, is considered serious. The event may be suspected from clinical symptoms or laboratory findings indicating an infection in a patient exposed to a Pfizer product. The terms “suspected transmission” and “transmission” are considered synonymous. These cases are considered unexpected and handled as serious expedited cases by PV personnel. Such cases are also considered for reporting as product defects, if appropriate.

Hospitalization

Hospitalization is defined as any initial admission (even if less than 24 hours) to a hospital or equivalent healthcare facility or any prolongation to an existing admission. Admission also includes transfer within the hospital to an acute/intensive care unit (e.g., from the psychiatric wing to a medical floor, medical floor to a coronary care unit, neurological floor to a tuberculosis unit). An emergency room visit does not necessarily constitute a hospitalization; however, an event leading to an emergency room visit should be assessed for medical importance.

Hospitalization in the absence of a medical AE is not in itself an AE and is not reportable. For example, the following reports of hospitalization without a medical AE are not to be reported.

- Social admission (e.g., patient has no place to sleep)
- Administrative admission (e.g., for yearly exam)
- Optional admission not associated with a precipitating medical AE (e.g., for elective cosmetic surgery)
- Hospitalization for observation without a medical AE

- Admission for treatment of a pre-existing condition not associated with the development of a new AE or with a worsening of the pre-existing condition (e.g., for work-up of persistent pre-treatment lab abnormality)
- Protocol-specified admission during clinical study (e.g., for a procedure required by the study protocol)

Scenarios necessitating reporting to Pfizer Safety within 24 hours

Scenarios involving exposure during pregnancy, exposure during breastfeeding, medication error, overdose, misuse, extravasation, lack of efficacy, and occupational exposure are described below.

Exposure during pregnancy

An exposure during pregnancy (EDP) occurs if:

1. A female becomes, or is found to be, pregnant either while receiving or having been exposed to (e.g., environmental) 3rd line treatment, or the female becomes, or is found to be, pregnant after discontinuing and/or being exposed to 3rd line treatment (maternal exposure).

An example of environmental exposure would be a case involving direct contact with a Pfizer product in a pregnant woman (e.g., a nurse reports that she is pregnant and has been exposed to chemotherapeutic products).

2. A male has been exposed, either due to treatment or environmental exposure to 3rd line treatment prior to or around the time of conception and/or is exposed during the partner pregnancy (paternal exposure).

As a general rule, prospective and retrospective exposure during pregnancy reports from any source are reportable irrespective of the presence of an associated AE and the procedures for SAE reporting should be followed.

If a study participant or study participant's partner becomes, or is found to be, pregnant during the study participant's treatment with 3rd line treatment, this information must be submitted to Pfizer, irrespective of whether an adverse event has occurred using the NIS AEM Report Form and the EDP Supplemental Form.

In addition, the information regarding environmental exposure to 3rd line treatment in a pregnant woman (e.g., a subject reports that she is pregnant and has been exposed to a cytotoxic product by inhalation or spillage) must be submitted using the NIS AEM Report

Form and the EDP supplemental form. This must be done irrespective of whether an AE has occurred.

Information submitted should include the anticipated date of delivery (see below for information related to termination of pregnancy).

Follow-up is conducted to obtain general information on the pregnancy, in addition, follow-up is conducted to obtain information on EDP outcome for all EDP reports with pregnancy outcome unknown. A pregnancy is followed until completion or until pregnancy termination (e.g., induced abortion) and Pfizer is notified of the outcome. This information is provided as a follow up to the initial EDP report. In the case of a live birth, the structural integrity of the neonate can be assessed at the time of birth. In the event of a termination, the reason(s) for termination should be specified and, if clinically possible, the structural integrity of the terminated fetus should be assessed by gross visual inspection (unless pre-procedure test findings are conclusive for a congenital anomaly and the findings are reported).

If the outcome of the pregnancy meets the criteria for an SAE (e.g., ectopic pregnancy, spontaneous abortion, intrauterine fetal demise, neonatal death, or congenital anomaly [in a live born, a terminated fetus, an intrauterine fetal demise, or a neonatal death]), the procedures for reporting SAEs should be followed.

Additional information about pregnancy outcomes that are reported as SAEs follows:

- Spontaneous abortion includes miscarriage and missed abortion;
- Neonatal deaths that occur within 1 month of birth should be reported, without regard to causality, as SAEs. In addition, infant deaths after 1 month should be reported as SAEs when the investigator assesses the infant death as related or possibly related to exposure to investigational product

Additional information regarding the exposure during pregnancy may be requested. Further follow-up of birth outcomes will be handled on a case-by-case basis (e.g., follow-up on preterm infants to identify developmental delays).

In the case of paternal exposure, the study participant will be provided with the Pregnant Partner Release of Information Form to deliver to his partner. It must be documented that the study participant was given this letter to provide to his partner.

Exposure during breastfeeding

Scenarios of exposure during breastfeeding must be reported, irrespective of the presence of an associated AE. An exposure during breastfeeding report is not created when a Pfizer drug specifically approved for use in breastfeeding women (e.g., vitamins) is administered in accord with authorized use. However, if the infant experiences an AE associated with such

a drug's administration, the AE is reported together with the exposure during breastfeeding.

Medication error

A medication error is any unintentional error in the prescribing, dispensing or administration of a medicinal product that may cause or lead to inappropriate medication use or patient harm while in the control of the health care professional, patient, or consumer. Such events may be related to professional practice, health care products, procedures, and systems including: prescribing; order communication; product labeling, packaging, and nomenclature; compounding; dispensing; distribution; administration; education; monitoring; and use.

Medication errors include:

- Near misses, involving or not involving a patient directly (e.g., inadvertent/erroneous administration, which is the accidental use of a product outside of labeling or prescription on the part of the healthcare provider or the patient/consumer);
- Confusion with regard to invented name (e.g., trade name, brand name).

The investigator must submit the following medication errors to Pfizer, irrespective of the presence of an associated AE/SAE :

- Medication errors involving patient exposure to the product, whether or not the medication error is accompanied by an AE.
- Medication errors that do not involve a patient directly (e.g., potential medication errors or near misses). When a medication error does not involve patient exposure to the product the following minimum criteria constitute a medication error report:
 - An identifiable reporter;
 - A suspect product;
 - The event medication error.

Overdose, Misuse, Extravasation

Reports of overdose, misuse, and extravasation associated with the use of a Pfizer product are reported to Pfizer by the investigator, irrespective of the presence of an associated AE/SAE.

Lack of Efficacy

Reports of lack of efficacy to a Pfizer product are reported to Pfizer by the investigator, irrespective of the presence of an associated AE/SAE or the indication for use of the Pfizer product.

Occupational Exposure

Reports of occupational exposure to a Pfizer product are reported to Pfizer by the investigator, irrespective of the presence of an associated AE/SAE.

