Adverse events will be summarized using the CTCAE.4.03 coding system. Event rates for single adverse events will be calculated based on the total number of patients valid for safety. Adverse events will be categorized according to relation, seriousness, CTCAE grade (version 4.03), and discontinuation of therapy, action taken and outcome. Special attention will be paid to serious adverse events and unexpected or unlisted ADRs.

Category counts and frequencies (percentages) will be calculated for overall tolerability.

Since the enrollment is after the initiation of the treatment, some information will be collected and analyzed retrospectively.

The best overall response is the best response recorded from the start of the study treatment until the end of treatment taking into account any requirement for confirmation.

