7. RESEARCH QUESTION AND OBJECTIVES

Research Question:

In this study, different from other studies in the literature, the data will be collected to observe the quality of life and efficacy after first line interferon alpha and second line TKI treatments.

Primary Objective:

- Measurement of health-related quality of life with targeted therapy used as 3rd line.
- Overall response rate at the end of follow up
- Median progression free survival according to RECIST version 1.1

Secondary Objectives:

- Overall survival rate
- Effect of quality of life on prognosis.
- Adverse events during 3rd line targeted treatment according to CTCAE.4.03
- Dose modifications due to adverse events
- Correlation between efficacy (overall response rate at month 12 and median PFS) and dose modifications due to adverse events
- Correlation between efficacy (overall response rate at month 12 and median PFS) and blood pressure

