8.2.1. Inclusion criteria

Patients must meet all of the following inclusion criteria to be eligible for inclusion in the study:

- Histologically confirmed metastatic renal cell cancer patients who have already been using targeted therapies for up to 1 months as 3rd line treatment
- Patients 18 years and older than 18 years
- Evidence of a personally signed and dated informed consent document indicating that the patient (or a legal representative) has been informed of all pertinent aspects of the study.

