8.3. Variables

The outcome variables for the objective(s) are time to treatment failure (from start of treatment to progression or permanent discontinuation), overall survival (from start of treatment to the date of last follow up or death), therapeutic response to therapy based on response evaluation criteria in solid tumors (RECIST version 1.1), and safety (type, incidence, severity of adverse events graded by the National Cancer Institute [NCI] CTCAE V.4.03)

Variable	Role	Data source(s)	Operational definition
Age, gender, height, weight, blood pressure, socio-demographic characteristics	Baseline characteristic	Medical Records	
Concomitant diseases	Baseline Characteristic	Medical Records	
Medication	Baseline Characteristic	Medical Records	
Histopathological findings	Baseline Characteristic	Medical Records / Pathology Reports	
Surgical Operations	Baseline Characteristic	Medical Records	
The cytokine (interferon alpha) usage in the first-line treatment, TKI usage in the 2 nd line treatment and the dosage and the duration of the treatment	Baseline Characteristic	Medical Records	
Metastatic features	Baseline Characteristic	Medical Records	
MSKCC risk factors	Baseline Characteristic Follow-up Characteristic	Medical Records	
3 rd line treatment	Baseline Characteristic Follow-up Characteristic	Medical Records	

	Close-out Characteristic		
The performance score before the second and third-line treatment		Medical Records	
The quality of life questionnaire (FKSI-15, EQ5D-3L, FKSI-DRS) on each visit	Baseline Characteristic Follow-up Characteristic Close –out Characteristic	Patient interview	
Blood pressure		Patient diary	
Other treatment during follow-up, if any, the dose and the duration	Follow-up Characteristic	Medical Records	
Treatment of the side effects, interruption of the treatment, dose reduction, dose-elevation	Baseline Characteristic Follow-up Characteristic	Medical Records	
Duration of PFS, OS and ORR	Follow-up Characteristic Close-out Characteristic	Medical Records	

Schedule Procedure	Initial visit	Follow-up 3.month	Follow-up 6.month	Follow-up 9.month	Follow-up 12.month	Survival Follow-up
Demographic data	X					
Histopathological Findigs	X					
Medical history	X					
Previous therapy of mRCC	X					
MSKCC Risk Factors	X	X	X	X	X	
Surgical Operations	X					
Metastases Information	X					
FKSI-15, EQ5D-3L, FKSI-DRS Questionnaire	X	X	X	X	X	
Evaluation of PFS,OS and ORR		X	X	X	X	
Concomitant medication	X	X	X	X	X	
Visit date	X	X	X	X	X	

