ECOG and Karnofsky Performance Status	X	X	X	X	X	
Prescribed TKI and dose	X					
3 rd line treatment	X	X	X	X	X	
Assessment of Response		X	X	X	X	
Adverse Events (Serious Adverse Events must be reported to the sponsor within 24 hours)		X	X	X	X	
Survival status						X

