8.7. Data analysis

Statistical analyses will be primarily of explorative and descriptive nature. All issues concerning patient validity, data consistency checks, permissible data modifications will be described in detail in the Data Management Plan.

Patients who took at least one dose of 3rd line treatment and have sufficient information whether they had an adverse event or not will be valid for safety analysis. Patients who took at least one dose of 3rd line treatment and have any information regarding efficacy of 3rd line treatment will be valid for intent-to-treat efficacy analysis.

Demographic data, baseline characteristics, diagnosis and prior treatment of RCC, concomitant diseases, and concomitant medication will be described with summary statistics such as mean, SD, minimum, 1, 5, 25, 75, 95, 99 percent quartiles, median, maximum for continuous variables, and category counts and frequencies (percentages) for

categorical variables. Concomitant diseases on the case report form correspond to MedDRA terms. Concomitant medication will be coded using WHO's drug dictionary.

Descriptive summaries of Kaplan-Meier (KM) estimates (including number of failed, number censored, 25th and 75th percentiles with respective 95% confidence level and median with 95% confidence level) and KM curves will be presented for time-to-event efficacy variables (PFS, TTP, time to treatment failure). Mean, SD, minimum, 1, 5, 25, 75, 95, 99 percent quartiles, median, maximum will be produced for duration of TKI treatment. Category counts and frequencies (percentages) will be calculated for tumor status at different visits and general subjective rating of efficacy of TKI from the treating physician.

Adverse events will be summarized using the MedDRA and the CTCAE coding system. Event rates for single adverse events will be calculated based on the total number of patients valid for safety. Adverse events will be categorized according to relation, seriousness, CTCAE grade (version 4.03), and discontinuation of therapy, action taken and outcome. Serious adverse events and unexpected or unlisted ADRs will be evaluated separately.

Category counts and frequencies (percentages) will be calculated for overall tolerability.

The factors, which might have impacted the duration of treatment, will be studied by retrospectively.

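### The plan does not ensure that adverse events between the first 3rd-line dose and consent are recorded and counted, although the safety objective and denominator run from the first dose

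*Combined protocol and SAP*

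**What the plan says.** **Eligibility.** Section 8.2.1 admits patients "who have already been using targeted therapies for up to 1 months as 3rd line treatment". Exposure before enrolment is therefore a condition of entry.

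**Safety start date.** The reporting-period paragraph of Section 10 offers two starting points: the first 3rd-line dose, or "the time of the patient's informed consent if s/he is already exposed to 3rd line treatment". The same sentence states what the period is for: "a report must be submitted to Pfizer Safety (or its designated representative) for any of the types of safety events listed". The table that opens Section 10 asks for all serious and non-serious adverse events on the case report form, with no start date of its own.

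**Schedule.** In Section 8.3 the row beginning "Adverse Events (Serious Adverse Events must be reported to the sponsor within 24 hours" is blank at the initial visit and marked at months 3, 6, 9 and 12.

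**Objective and analysis.** A secondary objective in Section 7 is "Adverse events during 3rd line targeted treatment according to CTCAE.4.03", with no restriction to the time after consent. Section 8.7 defines the safety set by at least one 3rd-line dose plus sufficient adverse-event information, and adds: "Event rates for single adverse events will be calculated based on the total number of patients valid for safety".

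**Passages that point the other way.** The variables table in Section 8.3 lists "Treatment of the side effects, interruption of the treatment, dose reduction, dose-elevation" as both a baseline and a follow-up characteristic, taken from medical records. The abstract says: "Since the enrollment is after the initiation of the treatment, some information will be collected and analyzed retrospectively".

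**The concern.** Numerator and denominator do not clearly cover the same period. A patient joins the denominator by virtue of the first dose, but the only start date a site can find for safety events is consent, and the first scheduled adverse-event entry is month 3. A site that follows the schedule and the Section 10 window literally would leave out an event that began and ended before consent. Another site, relying on the retrospective-collection sentence, might record it. With 25 centres (Section 8.1), capture could differ from site to site.

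At stake are two secondary objectives, adverse events and dose modifications due to them, and the planned correlations of those modifications with response and progression-free survival. Onset dates that were never collected cannot be restored at the analysis stage.

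**Working it through.** The plan gives no adverse-event rate, onset time or distribution of time from first dose to consent. There is thus no figure of the plan's own to reproduce. The check is a comparison of the passages, followed by an illustration.

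**Step 1: which start date applies?** Because Section 8.2.1 requires current 3rd-line use, the first-dose alternative in Section 10 fits no eligible patient. The start is always consent.

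**Step 2: what does each passage cover for the time from first dose to consent?**

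| Passage | Covers this time? |
|---|---|
| Section 7, objective | Yes: all 3rd-line treatment |
| Section 8.7, safety set and denominator | Yes: defined by first dose |
| Section 10, reporting period | No: starts at consent, but governs reports to the safety unit |
| Section 10, case-report-form column | Not stated |
| Section 8.3, schedule, adverse-event row | No entry at initial visit |
| Section 8.3, variables table | In part: treatment of side effects and dose changes, not event type, grade or onset |
| Abstract, retrospective collection | In part: events neither named nor excluded |

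The passages disagree, and none says outright that events before consent are recorded and counted.

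**Step 3: direction.** If such events are left out, the numerator can lose patients while the denominator stays the same. The bias can only be downward.

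**Step 4: illustrative size.** Let
- f = share of affected patients whose only occurrence falls in month 1 of treatment;
- m = fraction of that month elapsed before consent.

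Assume that nothing before consent is counted and that these occurrences are spread evenly within the month and over before consent if they began before it. Then

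observed incidence = true incidence × (1 − f × m), so relative understatement = f × m.

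Both f and m are assumptions. The lowest f, 1/13, corresponds to even onset over 13 months (up to 1 month before enrolment plus 12 months of follow-up). The values 0.25 and 0.50 represent early clustering.

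| f | m = 0 | m = 0.5 | m = 1 |
|---|---|---|---|
| 1/13 | 0 | 3.8% | 7.7% |
| 0.25 | 0 | 12.5% | 25% |
| 0.50 | 0 | 25% | 50% |

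Example with an assumed true incidence of 20%, or 0.20 × 152 = 30.4 patients. At m = 1 the observed incidence would be:
- f = 1/13: 0.20 × (1 − 0.077) = 18.5%
- f = 0.25: 0.20 × 0.75 = 15.0%
- f = 0.50: 0.20 × 0.50 = 10.0%

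An event that persists or recurs after consent is still counted, which is why f is restricted to patients with no later occurrence.

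**The case against.** The strongest reply is that the plan does not omit the early period. The Section 10 window concerns reports to the sponsor's safety unit, not entries on the case report form or the analysis. The variables table already places side-effect treatment, interruptions and dose changes at baseline. The schedule marks the 3rd-line treatment and concomitant-medication rows at the initial visit. The abstract's sentence on retrospective collection follows directly after its adverse-event and tolerability paragraphs. A mark at month 3 shows when events are entered, not how far back they may reach.

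Much of this stands. A reader might infer that first-month toxicity is missed, that rates are understated, and that early dose modifications are lost. The documents do not support any of these as fact. The first two hold only if nothing before consent is recorded, which the text does not establish. The third conflicts with the variables table. Nor is a full month at risk for everyone: the gap is at most one month. A specific loss figure cannot be defended either, because the documents contain no onset data.

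What the reply does not do is close the gap. An event that was neither treated nor followed by a dose change would not appear under the variables-table entry, and that entry gives no grade or onset date. The retrospective sentence does not say which information it means. Neither fits a blank adverse-event cell at the initial visit.

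**Conclusion.** The concern holds as a failure to ensure capture, not as proven loss. All eligible patients are pre-exposed, the only stated safety start date for them is consent, and the schedule has no adverse-event entry at the initial visit, while the objective and denominator count from the first dose. If events before consent are not counted, per-patient rates are biased downward by an unknown amount. The illustration gives about 4% to 50% in relative terms for f from 1/13 to 0.5 and m from 0.5 to 1. It falls to zero if consent coincides with the first dose, or if earlier events are in fact recorded. The range depends wholly on assumed values of f and m and should not be read as an estimate. The objective affected is secondary and descriptive, but the remedy changes what is collected, so it should be made and not left to interpretation by sites.

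**What to change.** 1. Mark Adverse Events at the initial visit in the Section 8.3 schedule.
2. At that visit, record from the medical file all adverse events from the first 3rd-line dose to consent, with CTCAE grade, onset date and action taken, flagged as before consent. Say in Section 8.7 and the abstract that this is part of the retrospective collection.
3. Make the schedule's handling of dose modifications consistent with the variables table, which already treats them as baseline data.
4. In Section 8.7, report incidence from the first dose, with a second table restricted to events after consent. Label any after-consent rate as such and use time at risk that also starts at consent.
5. Leave the Section 10 window for reports to the sponsor unchanged.

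**Cost.** About one additional case-report-form page, filled from records that are already the data source (Section 8.4), with source verification of all patients already planned (Section 8.8). No extra diagnostic or monitoring procedure is needed.

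**What it does not cure.** Retrospectively recorded events will be less complete, hence the flag and the second table. Patients who stopped treatment or died before they could consent are still not represented. The plan should state this as a limitation.
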